3. BASELINE DATA

The following baseline data will be collected online via the trial website:

- **Demographic information:** Date of birth, gender, ethnicity, and level of education. Also self-reported height and weight, and body mass index (BMI) will be calculated.
- **Smoking history:** Age when started, number of cigarettes smoked per day, number of years as regular smoker, number of previous attempts to give up in past 12 months (and the longest time they stayed quit and the method used), type of cigarettes smoked per day (e.g. roll-your-own or factory-made) and pack size and how long pack lasts (for roll-your-own users), and whether they had cut down the number of cigarettes they smoked in the past 12 months.

- **Motivation to quit** in the next two weeks, measured using a five-point Likert Scale, where 1=very low motivation and 5=very high.
- **Level of cigarette dependence:** will be determined using the Heaviness of Smoking Index (HSI), which is a two-item measure based on the number of cigarettes smoked per day (categorised as: 0=10 or fewer, 1=11-20, 2=21-30, 3=31 or more) and the time to first cigarette of the day. The HSI total score is calculated by summing these two items and has range 0 to 6 where higher scores indicate greater dependence severity. The HSI total score will be categorised as low addiction (0-2), moderate addiction (3-4) and high addiction (5-6).
- **Other smoking related information:** household smoking, self-rated chances of quitting (measured using a five-point Likert Scale, where 1=extremely low and 5=extremely high), and whether they are around others that use e-cigarettes.
- **General Health:** Self-reported shortness of breath, cough, asthma, chronic pain, and Chronic Obstructive Pulmonary Disease (COPD), and current or history of mental health (including depression, schizophrenia, and anxiety).
- **Alcohol use:** Measured using the Alcohol Use Disorders Identification Test (AUDIT-C). The AUDIT-C score is calculated by summing all three items and has range 0 to 12 where higher scores indicate greater risk of alcohol dependence. Note participants that tick 'Never' for the first AUDIT-C item (How often do you drink alcohol in the past year) then skip the next two AUDIT-C items, so for these AUDIT-C score to be set to value 0. For men, an AUDIT-C score ≥ 4 indicates an increased risk of hazardous drinking or alcohol dependence, while in women it is a score of ≥ 3 . And an AUDIT-C score ≥ 8 indicates a very high risk for both men and women.
- **Health related quality of life:** measured using the NZ EQ-5D
- **Signs and symptoms of nicotine withdrawal and urge to smoke:** measured using the Mood and Physical Symptoms Scale (MPSS) which consists of the following:
 - 5-point ratings of depressed mood, irritability, restlessness, hunger and difficulty concentrating. MPSS score is calculated by summing all 5 items and has a range of 5 to 25 where higher scores indicate greater nicotine withdrawal.
 - 6-point ratings of time spent with urges to smoke and strength of urges to smoke. Note the strength of urges question has values 1 to 5. Participants who tick 'Not at all' for time spent with urges to smoke have to then skip to the next section of questions and don't answer the question on strength of urges. So for these participants need to set strength of urges to equal value 0. [Therefore, this question will then have values 0 to 5]. The urge score is calculated by summing the two urges questions and has a range 0 to 10 where higher scores indicate greater urge to smoke.
- **Cannabis use:** Participants will be asked if they have used cannabis for recreational or non-medical purposes in the last 12 months.

4. STUDY OUTCOMES

4.1. Primary outcome

Verified six-month continuous abstinence (using Russell Standard) defined as self-report of smoking not more than five cigarettes from the Quit date and confirmed by an expired air carbon-monoxide (CO) measurement with a Bedfont Smokerlyzer (≤ 9 ppm signifying abstinence). Biochemical validation of self-reported cessation for Auckland participants will involve a researcher visiting participants within 72 hours if they claim to be abstinent, to obtain a CO reading. For participants outside of Auckland who self-report that they are smokefree, verbal consent will be sought from them to provide their contact details to their region's community-based smoking cessation service, so that they can undertake the CO monitoring within 72 hours. Sensitivity analysis will be undertaken looking at different cut-offs for the CO measurement, given lack of consensus about the best reading to use

4.2. Secondary outcomes

The following secondary outcome measures will be collected over the phone on the quit date and at one, three, six and 12 months post-quit date:

- **Continuous abstinence** rates (using Russell standard) defined as self-report of smoking not more than five cigarettes in total from quit date (not collected at quit date)

Note if previous follow-up forms state they smoke more than 5 cigarettes since Quit date then subsequent follow-ups will be set to Not quit. Also, if a follow-up form is missing but the subsequent follow-up form(s) says they have smoked less than 5 cigarettes since Quit date (and no other previous follow-up forms have said they smoke more than 5 cigarettes since Quit date), then the missing follow-up form will have continuous abstinence set to 'Quit'.

- **Seven-day self-reported point prevalence abstinence** rates defined as no cigarettes, not even a single puff in the last seven days (not collected at quit date)
- **Change in average number of cigarettes smoked per day (CPD)** for participants still smoking
- **Proportion of participants who have significantly reduced smoking level** defined as reducing consumption by at least 25% (in terms of numbers of cigarettes per day)
- **Time to first lapse** (six and 12 months) defined as time to first cigarette smoked (even a single puff). From first follow-up form with question "Have you smoked any cigarettes at all in the last seven days, even a single puff?" equal to "Yes". Duration is calculated as the days since actual quit day to date of first lapse in the follow-up form.

Participants that withdraw will be censored on the last available visit, and participants that have not lapsed by the six (or 12) month follow-up will be censored on the six (or 12) months visit date. Note the first follow-up form with a lapse date will be taken since this will be more accurately remembered by participants than later visits.

- **Time to first relapse** defined as time to smoking more than five cigarettes a day for three or more days in a row. From first follow-up form with question “Have you smoked more than 5 cigarettes per day for 3 or more days in a row?” equal to “Yes”. Duration is calculated as the days since actual quit day to date of first relapse in the follow-up form

Participants that withdraw will be censored on the last available visit, and participants that have not relapsed by the six (or 12) month follow-up will be censored on the six (or 12) months visit date. Note the first follow-up form with a relapse date will be taken since this will be more accurately remembered by participants than later visits.

- **Use of other medication and other methods of cessation** (participants will be asked about their use of other methods of cessation, such as NRT, Zyban, clonidine, nortriptyline, e-cigarettes, acupuncture etc)
- **Health-related quality of life** (three, six and 12 months) measured using the New Zealand EQ-5D
- **Treatment use and compliance** (quit date, one and three months): use of the allocated product. This will include daily use (and reasons for not using daily), and number of pills or pods remaining.

For participants allocated to cytisine, compliance is defined as having taken $\geq 80\%$ of the required number of tablets over the three-month intervention period.

- **Signs and symptoms of nicotine withdrawal, and urge to smoke** (three months): measured using the MPSS
- **Crossover** where participants in the cytisine-only group will be asked whether they accessed and used an e-cigarette (with or without nicotine) during the six (or 12) month study period, and participants in the e-cigarette group will be asked whether they accessed and used cytisine during the trial.
- **Change in e-cigarette use**: Participants allocated to the e-cigarette groups will be asked whether they changed the type of e-cigarette device and/or the nicotine strength and/or flavor they used in the e-cigarettes provided. If they did, they will be asked when they did this, and what the device type, nicotine strength and/or flavor was.
- **Dual use** (not collected at quit date): defined as daily use of both their allocated treatment and continued smoking of cigarettes every day.
- **Continuation of product use** (at six and 12 months in a subsample) defined as continued use of their allocated treatment after the end of the designed three-month treatment period.
- **Acceptability of the product** (three months): Participants will be asked for their views on the use of their allocated product as a cessation aid
- **Recommendations** (three months): Participants will be asked whether they would recommend their allocated treatment to another smoker who wanted to quit.
- **Adverse events and serious adverse events**: self-reported adverse events are collected at each follow-up call, with adverse events coded using MedDRA. In addition, participants can at any time report an adverse event via a web-based adverse event diary.

- **Change from baseline in weight and body mass index** (three and six months)
- **Change from baseline in general health** (three, six and 12 months): shortness of breath, cough, asthma, chronic pain, COPD, and mental health. Measured for participants who answered Yes to the general health question at baseline, and is measured using a five-point scale (much worse, a bit worse, about the same, a bit better, much better).
- **Concomitant medication:** other medications taken during the course of the study
- **Cost outcomes:** cost-per- quitter, cost-per-person reducing their daily cigarette consumption, and the incremental cost-effectiveness ratio
- **Text-based behavioral support STOMP program received:** total number received up until end of the six month follow-up or they opt out of receiving the messages.

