Participants will be called on their quit date to verify they are quitting on that day (and to collect outcome data). If a participant states that they are not quitting on the scheduled 'quit date', they will be given one chance to reset their quit date within the next seven days, with this date becoming their new 'quit date' (which will trigger the scheduling of all subsequent follow-up calls). For participants who are unable to be contacted at quit date, their 'quit date' will be set in the system as six days after they received their courier pack (which will trigger the scheduling of all subsequent follow-up calls). Participants will be advised to continue with their allocated treatment irrespective of any lapses back to smoking.

Outcome assessments will be undertaken at one, three, and six months after the Quit date, and at 12 months in a subsample. At the six-month follow-up, in-person carbon monoxide tests will be performed for participants who live in the Auckland region to verify self-reported continuous smoking abstinence.

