7.5. Primary outcome analysis

The proportion of participants that have been biochemically verified as continuously abstinent at six months by group will be analysed using log-binomial regression, and the risk in each group, relative risks, absolute risk differences, and corresponding 95% confidence intervals will be calculated. All analyses for the

primary outcome will be ITT (unless otherwise stated) and include all randomised participants. Missing outcomes will be imputed using multiple imputation assuming the data is missing at random. Multiple imputed datasets will be created (n=50) and the imputation model will include baseline age, sex, and group, and the fully conditional specification logistic regression method will be used to impute the missing outcomes. The imputed datasets will be analysed using log-binomial regression and combined to output one inference. Adjusted analyses for potential covariates will be conducted if needed.

To check the robustness of the primary outcome the following sensitivity analyses will be conducted:

- self-reported continuous abstinence at 6 months (not biochemically verified)
- using the following varying cut-offs used for CO measurements: ≤ 3 ppm, ≤ 5 ppm, ≤ 8 ppm

The following sensitivity analyses will also be conducted for the primary outcome where groups will be compared using chi-squared tests:

- complete case analysis
- per protocol analyses where participants that have any major protocol violations will be excluded (see 6.2)
- assuming all missing outcomes are still smoking instead of using multiple imputation

Tests for heterogeneity will be used to examine if there is any difference in the groups on the unadjusted primary outcome for the following subgroups: baseline age (will be dichotomised based on the median), sex, ethnicity (Māori, non-Māori), education (< 12 years of attending school, 12 or more years of attending school), type of cigarettes smoked (RYO, factory made, both), AUDIT-C (low, high), cannabis use, motivation to quit, level of cigarette dependence (using HSI), and level of behavioural support received (will be categorised based on the data). Subgroup analyses will also be conducted by batch number of product received (Batch 1: early 2022, Batch 2: early 2023) to assess if there were any differences by batch.

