7.6. Secondary outcomes analysis

Descriptive summary statistics for each follow-up visit and group will be presented for all secondary outcomes. For all secondary outcomes (unless otherwise stated) participants with missing outcome data will be excluded from the analyses.

Incidence rates, risk difference, relative risks and 95% confidence intervals will be calculated for self-reported continuous abstinence (not biochemically verified), seven-day point prevalence abstinence and reduced CPD consumption by at least 50% outcomes at each follow-up visit. Both complete case analysis and ITT analysis (where missing outcomes will be imputed using the same multiple imputation method described above for the primary outcome) will be conducted.

MPSS at 3 months (for 6-month continuous abstainers only) will be analysed using linear regression and include baseline MPSS in the model. The change from baseline in each of the repeated continuous outcomes (average number of cigarettes smoked each day for smokers, weight and BMI) will be analysed using mixed models. Each model will include group and the baseline measure. The appropriate covariance structure to be used will be assessed by the likelihood ratio test. The method of maximum likelihood will be employed to ensure patients with missing data are included in the model assuming the data is missing at random. However, if all follow-up data is missing then the participant will be excluded from the analyses. Intervention by visit interaction effects will be tested. Note the

distribution of these continuous outcomes will be first assessed for normality and skewed data will be subjected to an appropriate transformation before analysis. Non-parametric analysis (Mann-Whitney tests) will be used for the continuous outcomes if data is skewed and cannot be transformed to be normally distributed.

The time to first lapse and relapse outcomes will be analysed using Kaplan-Meier curves, the log rank test, and Cox proportional hazards regression analysis.

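### Applied as written, the 'Not quit' carry-forward makes 12-month continuous abstinence rates and risk differences too small, because abstainers have 12-month values only in the subsample

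*SAP*

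**What the plan says.** - **Who is followed to 12 months.** SAP section 2: "Outcome assessments will be undertaken at one, three, and six months after the Quit date, and at 12 months in a subsample". The SAP gives neither the subsample's size nor how it is chosen.
- **Carry-forward of failure.** Section 4.2 lists self-reported continuous abstinence as an outcome up to 12 months and adds: "if previous follow-up forms state they smoke more than 5 cigarettes since Quit date then subsequent follow-ups will be set to Not quit".
- **Back-fill of success.** The companion rule in section 4.2 works only "if a follow-up form is missing but the subsequent follow-up form(s) says they have smoked less than 5 cigarettes since Quit date", provided no earlier form reports failure. It needs a later form, and no visit follows 12 months.
- **Which visits are analysed, and how.** Section 7.6 calculates rates, risk differences and relative risks for continuous abstinence, point prevalence abstinence and "reduced CPD consumption by at least 50% outcomes at each follow-up visit". It plans a complete-case analysis and an ITT analysis "where missing outcomes will be imputed using the same multiple imputation method described above for the primary outcome".
- **Imputation model.** Section 7.5: "the imputation model will include baseline age, sex, and group".
- **Denominator.** Section 6.1 defines ITT as everyone randomised. No section limits the 12-month denominator to the subsample.

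**The concern.** No single carried-forward value is wrong: a person who has already smoked more than five cigarettes since the quit date cannot be continuously abstinent later. The difficulty is who ends up with a value at 12 months. Under the stated rules, failure by six months fixes the 12-month outcome for everyone, while six-month abstinence leaves it unknown unless the person is in the subsample and responds. Whether the outcome is observed therefore depends on the smoking course, even if the subsample is drawn at random.

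The complete-case set then holds all the earlier failures but only a fraction of the abstainers. The imputed analysis has no variable that separates the two kinds of participant, so it fills the abstainers' gaps from the same failure-heavy pool. At stake are the 12-month abstinence rates and both planned between-group comparisons.

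**Working it through.** The SAP gives no 12-month figure to reproduce.

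**Inputs**
- A, six-month abstinence: 25% combination, 12% cytisine, 9% e-cigarette (SAP 2.4). These are planning rates for verified abstinence, used here for a self-reported outcome as an illustration only.
- k, share of six-month abstainers still abstinent at 12 months: 0.7, assumed.
- s, share of six-month abstainers who have a 12-month form: not in the SAP; shown from 0.25 to 1. Non-response within the subsample lowers s further.
- Data up to six months are otherwise taken as complete.

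**Formulas**
- True 12-month rate = A × k.
- Complete-case rate under the rule = s × A × k / ((1 − A) + s × A).

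**Worked case, s = 0.5, 300 per arm**
- Combination: 225 earlier failures, all set to 'Not quit'. Of 75 abstainers, 37.5 have a 12-month form and 26.25 are still abstinent. Rate = 26.25 / 262.5 = 10.0%; truth = 52.5 / 300 = 17.5%.
- Cytisine: 264 failures and 36 abstainers, of whom 18 have a form and 12.6 are still abstinent. Rate = 12.6 / 282 = 4.5%; truth = 25.2 / 300 = 8.4%.

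**Range over s, combination vs cytisine**

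| s | Combination | Cytisine | RD (points) | RR |
|---|---|---|---|---|
| 1 (no bias) | 17.5% | 8.4% | 9.1 | 2.08 |
| 0.75 | 14.0% | 6.5% | 7.5 | 2.16 |
| 0.5 | 10.0% | 4.5% | 5.5 | 2.24 |
| 0.25 | 5.4% | 2.3% | 3.1 | 2.33 |

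Against the e-cigarette arm at s = 0.5, 17.5% vs 6.3% (RD 11.2, RR 2.78) becomes 10.0% vs 3.3% (RD 6.7, RR 3.03).

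**Why the relative risk moves the other way.** Each arm's rate is multiplied by s / ((1 − A) + s × A), and k cancels. At s = 0.5 this is 0.5 / 0.875 = 0.57 for combination and 0.5 / 0.94 = 0.53 for cytisine. The arm with fewer abstainers shrinks more.

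**Imputation.** In the worked combination arm, 37.5 participants lack a value. Imputing from group at 10.0% adds 3.75 abstainers: (26.25 + 3.75) / 300 = 10.0%, unchanged. Imputing with six-month status known uses 70%: (26.25 + 26.25) / 300 = 17.5%, the truth.

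A simulation agrees (400 runs, 50 imputations, 300 per arm, k = 0.8, s = 0.5, random subsample, age and sex uninformative):

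| Analysis | Combination | Cytisine |
|---|---|---|
| Truth | 20.1% | 9.5% |
| Complete case under the rule | 11.6% | 5.1% |
| Imputation from group only | 11.6% | 5.1% |
| Subsample only | 20.3% | 9.5% |
| Imputation with six-month status | 20.1% | 9.4% |

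**The case against.** The strongest reply is that the note in section 4.2 is about follow-up forms. A participant outside the subsample has no 12-month form due, so there is nothing to set to 'Not quit' and nothing missing to impute. A sensible analyst would use the subsample alone, and the asymmetry would not arise. That reading is reasonable, and the text does not exclude it. But the SAP does not state it, and the all-randomised ITT definition together with analysis at every visit points the other way. Section 5 has programs written on dummy data before data-lock, so a literal coding of the rule is a real possibility.

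It is also fair that the decisive input, s, is not in the SAP. The protocol may give it. If every six-month abstainer were in the subsample and responded, s would be 1 and there would be no bias.

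A reader might draw three stronger conclusions that the document does not support:
- **That imputation causes the bias.** The complete-case analysis has it equally. Imputation only fails to remove it.
- **That the bias depends on the subsample fraction alone, or dilutes every effect measure.** The shrinkage also depends on each arm's abstinence rate, and the relative risk rises.
- **That the trial's main result is at risk.** The rule belongs to a secondary self-reported outcome, and all participants are due for follow-up at six months.

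**Conclusion.** The point holds as a defect of specification. Followed literally for all randomised participants, the SAP's rules understate 12-month continuous abstinence and the risk differences, slightly inflate the relative risk, and leave the imputed analysis with the same error. Under an assumed half subsample the reported rates would be about 53% to 57% of the truth in the cytisine and combination arms, whatever share of six-month abstainers remains abstinent. With a quarter subsample the risk difference between these arms would fall from 9.1 to 3.1 points.

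These figures illustrate the mechanism and are not estimates for this trial. They rest on the planning rates, 70% retention, an assumed subsample share unrelated to smoking outcome, and application of the rule outside the subsample. A bias in the trial's results is therefore not established; what is established is that the text permits it and nothing in the text prevents it. The change should be made before data-lock, but it concerns only one secondary outcome at one visit.

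**What to change.** In SAP sections 4.2 and 7.6:

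1. State how the 12-month subsample is selected, or refer to where this is fixed.
2. If selection is unrelated to smoking outcome, define the 12-month analysis set as the randomised participants selected for the subsample. Apply carry-forward and imputation only within it.
3. Add last known continuous-abstinence status to the imputation model for this outcome. This is needed within the subsample too, because abstainers who do not respond are missing while earlier failures are not. Everyone already set to 'Not quit' has a known outcome, so the simplest form is to impute only among those not yet known to have failed.
4. If selection depends on six-month status, do not restrict. Keep all randomised participants and impute with six-month status in the model. Restriction would then condition on a post-randomisation outcome: on the assumptions used here, a subsample of abstainers only would show 70% in both arms and erase the difference.

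The cost is SAP wording and a small change to the imputation program. No new data are needed, and the primary analysis is unchanged.

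### The back-fill rule for missing follow-up forms uses a stricter cut-off (fewer than five cigarettes) than the abstinence definition (five or fewer), so a later total of exactly five leaves an earlier form missing when its status is known

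*SAP*

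**What the plan says.** SAP section 4.2 defines the secondary outcome of continuous abstinence as "self-report of smoking not more than five cigarettes in total from quit date". Section 4.1 uses the same limit for the self-report part of the primary outcome: "self-report of smoking not more than five cigarettes from the Quit date". Under both, exactly five cigarettes is abstinent.

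A note under the secondary definition gives two derivation rules.

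- **Carry-forward to *Not quit*:** "if previous follow-up forms state they smoke more than 5 cigarettes since Quit date then subsequent follow-ups will be set to Not quit".
- **Back-fill to *Quit*:** a missing form is set to *Quit* if a later form "says they have smoked less than 5 cigarettes since Quit date", provided that "no other previous follow-up forms have said they smoke more than 5 cigarettes since Quit date".

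Section 7.6 says what happens to a form that stays missing. The default for secondary outcomes is that "participants with missing outcome data will be excluded from the analyses". Self-reported continuous abstinence is analysed both as complete cases and by intention to treat, "where missing outcomes will be imputed using the same multiple imputation method described above for the primary outcome".

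**The concern.** The definition and the carry-forward rule split the cigarette count into five or fewer and more than five. These two sets are complementary and leave nothing over. The proviso in the back-fill rule uses the same split. Only the condition on the later form departs from it, by requiring fewer than five. The mismatch lies within a single sentence of the SAP.

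This matters because the note is an instruction for assigning outcome values. Followed literally, it leaves as missing a status that the SAP's own definition determines. It also allows two programmers to derive different datasets, one coding the phrase as written and the other coding the definition. Section 5 plans for programming to begin on dummy data well before data-lock, so the wording can be settled before anyone has to decide it with outcomes in view.

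**Working it through.** The plan states no figure on this point, so there is nothing to reproduce. The check applies each written rule to a cumulative total *c* on a later form, with one earlier form missing and no earlier form above five.

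**Inputs**

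- Abstinent: c ≤ 5 (sections 4.1 and 4.2).
- Carry-forward to *Not quit*: c > 5 (section 4.2).
- Back-fill, condition on the later form: c < 5 (section 4.2).
- Back-fill, condition on earlier forms: none above 5 (section 4.2), met here by construction.

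**Rules applied**

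| c on later form | Later form (c ≤ 5?) | Back-fill condition (c < 5?) | Missing earlier form |
|---|---|---|---|
| 4 | 4 ≤ 5, *Quit* | 4 < 5, met | set to *Quit* |
| 5 | 5 ≤ 5, *Quit* | 5 < 5 is false, not met | stays missing |
| 6 | 6 > 5, *Not quit* | 6 < 5 is false, not met | stays missing, as it should |

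The gap is exactly c = 5.

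**Is the missing status known at c = 5?** The count runs from the quit date and cannot fall over time. If the total is 5 at the later visit, the total at any earlier visit is at most 5. By the definition the earlier visit is therefore abstinent, just as it is for c = 4. At c = 6 the earlier total could lie on either side of the limit, so leaving the form missing is right.

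**Which visits can be affected?** Forms are taken at one, three and six months, and at 12 months in a subsample (section 2). Back-filling needs a later form.

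- One month: a three-, six- or 12-month form can trigger the rule.
- Three months: a six- or 12-month form can.
- Six months: only a 12-month form can, so only in the subsample. By that route the self-report sensitivity analysis in section 7.5 could also be touched.

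**What happens to the form left missing?** In the complete-case analysis it is dropped. In the intention-to-treat analysis it is imputed. The imputation model described in section 7.5 names baseline age, sex and group, and does not name the later form. A participant known to be abstinent could therefore be imputed as smoking in some of the 50 datasets.

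**After the correction.** With the back-fill condition at c ≤ 5, the total of 5 meets it and the earlier form becomes *Quit*. The results for 4 and 6 do not change.

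**The case against.** The best case for leaving the text alone has three parts.

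- **It is probably a slip.** The definition directly above the note, the carry-forward rule and the back-fill proviso all agree. A programmer who reads the note as a whole would probably apply the definition. That is plausible, but nothing in the SAP corrects the phrase, and a derivation rule should not rely on the programmer overriding it.
- **The gap may have no practical effect.** The SAP does not show the abstinence question. The relapse question quoted in section 4.2 is a yes/no item. If the abstinence item is likewise answered only as above or not above five, exactly five cannot be separated from four, and the gap disappears. This stands: the consequence depends on the form recording a count. The wording would still disagree with the definition.
- **The number of participants is negligible.** An affected participant needs a total of exactly five, a missed earlier visit and a completed later one. Both complete-case and imputed analyses are planned. This also stands as to size, although both analyses mishandle such a form, so having both does not cure it.

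Three stronger readings are tempting, and the SAP does not support them. A reader might infer that the two rules give the same participant opposite classifications. They do not: no rule calls exactly five *Not quit*, the later form is *Quit*, and only the earlier form is left unresolved. A reader might infer from the shared threshold in section 4.1 that the primary outcome is at risk. That outcome also needs a carbon monoxide reading, which back-filling a form cannot supply. Finally, a reader might take more than five cigarettes as the relapse criterion and see a conflict there too. Relapse in section 4.2 is a separate outcome, based on a daily amount sustained over at least three consecutive days and not on a total since the quit date.

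**Conclusion.** The inconsistency is real and internal to section 4.2. Read literally, the back-fill rule leaves one count, exactly five, without the status that the SAP's definition implies for the missed earlier visit. The direction is clear: each affected form is a known abstainer who is excluded or imputed.

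The effect is small. No number of participants can be derived, because the SAP gives no frequency for such totals or for missed visits of this pattern. It is limited to self-reported continuous abstinence, chiefly at one and three months.

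The conclusion rests on three assumptions: the form records a count, the phrase is programmed as written, and the self-reported total is taken as cumulative from the quit date, as the definition says. This is a minor correction that is worth making before the derivation code is final.

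**What to change.** In the back-fill rule in section 4.2, replace less than 5 cigarettes with not more than five cigarettes, so that its condition on the later form matches the definition. The carry-forward rule and the proviso on earlier forms need no change.

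The cost is a few words in the SAP and, if the derivation has already been coded, one comparison operator. No sample size, outcome definition, data collection or analysis model changes.
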